research protocol, that is, pretest (week 1), intermediate test 1 (week 6), test intermediate 2 (week 11) and posttest (week 16). Likewise, the groups formed randomly and the confrontation between them determined by chance at all test will be respected. If for any reason a participant cannot take the test due to any circumstance (absence at the session, physical discomfort, momentary bruises, injury or unexpected situations), his replacement will be arranged with IUEFD student with experience as soccer players and who previously know the protocol to complete the gap, or with soccer players who are on trial at the club and who are not part of the comparison groups. The tests will be carried out on Wednesday from 6 to 8 in the morning in the respective weeks (1, 6, 11 and 16).

Once the tests have been completed and duly filmed, the respective videos will be passed on to the evaluator (video analyst) who will download the videos, analyze the different actions and behaviors developed by each of the participants through the LINCE PLUS video analysis software and record the data in Excel files in the database created for this purpose. This database will be created in such a way that a code is generated for the participants and no one can identify who the information registered and consigned there corresponds to (except the main researcher) who will save it on their personal computer, on a hard drive to keep copy and in the cloud. These files will be kept with a password, which only the principal researcher will know.

The information and data resulting from the respective analyzes carried out by the evaluator will be sent to the statistician who will proceed to carry out the respective analysis and application of tests in accordance with the data treatment that appears in the data analysis section.

Prior to carrying out the FOCOS test that evaluates the primary and secondary outcomes and, prior to the execution of the tests that evaluate executive functions (exploratory outcome), the following question will be asked to the participants: from 0 to 100, ¿How mentally fatigued are you? Being 0 (not at all fatigued) and 100 (maximum fatigue).

The evaluations of week 1 were carried out on two different days and in the following order: the first day the survey was carried out, mass, height, mental fatigue and finally, the tests were applied to assess the executive functions, for which participants were

summoned by groups of 4 every hour. Total application time from full battery was approximately 60 minutes. On the second day, the FOCOS field test was carried out and all the participants were summoned at 6 in the morning. In the intermediate tests 1 (week 6) and 2 (week 11) only the evaluations will be carried out through FOCOS. Finally, the post-test evaluations (week 16) will be carried out in the same way as in the pre-test, that is, they will be carried out on two different days and in the following order: the first day the tests will be applied to assess the executive functions and mental fatigue, on the second day, the field test (FOCOS) will be carried out, for which all the participants will be summoned at 6 in the morning.

Bias Control

To control biases in the different stages of the study (planning, execution, and data analysis), different strategies and actions were established to obtain reliable results. Bias control was carried out as follows:

Control of Allocation Biases (Randomization Biases)

To avoid these biases, the participants were randomized to two comparison groups (GE and CG) as previously described in the randomization process.

Control of Information Biases (Systematic Biases)

To avoid these biases, reliable and valid protocols and tests are used, in addition, the evaluation protocols were standardized (pretest, intermediate test 1, intermediate test 2 and posttest), which will be carried out under similar conditions, with the same equipment and by the same evaluators). In the same way, the equipment and instruments were calibrated in accordance with quality norms and standards. It is important to mention that the personnel that carry out the evaluations and interventions are experts in their respective areas and that those necessary for the development of a protocol or intervention were trained. In addition, the evaluator of the actions related to the PTK and the IE (offensive, defensive, and global) must demonstrate and achieve a good stability, which will be obtained and calculated through test-retest, once the evaluator achieves a score for above 0.6 the PTK evaluation process will continue in the research.

Confounding Bias Control

To avoid these biases, confounding variables (age, sporting age, playing position, socioeconomic status, educational level, mass, BMI, and mental fatigue) will be controlled.

The study has masking (blinding) at two levels (assessments and data analysis).

Analysis of data

To establish the distribution of the data of the quantitative variables, the Shapiro-Wilk test will be applied. The variables that present a normal distribution will be summarized with means and standard deviation. Variables that present a non-normal distribution will be summarized with medians and interquartile ranges. Likewise, the qualitative variables will be presented in absolute and relative frequency tables.

To establish the behavior of the offensive, defensive, and global IE, a repeated measures design will be carried out that includes 4 evaluations over time (pretest, intermediate test 1, intermediate test 2 and posttest). For this, an ANOVA of repeated measures or the Friedman test will be used according to the normality of the variables, in addition, the assumption of homogeneity of the variances will be evaluated based on the Levene statistic. Since different dependent variables will be evaluated, a multivariate analysis of variance (MANOVA) will also be performed.

For the variables related to executive functions, an intragroup analysis of each of the groups (GE and GC) will be carried out, comparing the pretest and posttest values to establish possible differences, for which the dependent student t test or the Wilcoxon test of according to its distribution. In addition, an intergroup analysis will be carried out to compare the possible differences between the groups (GE and GC), for which the student t test for independent samples or the Mann Whitney U test will be applied according to the distribution of the variables. Similarly, confidence intervals (CI95) and two-tailed effect sizes will be reported, with alpha (α) set to 0.05 and statistical power 0.8 (1- β). The statistical significance value is set at $p \leq 0.05$. An analysis of the information will be carried out using the statistical package SPSS version 27 and the software R free version 4.0. Procedures will be carried out to detect possible inconsistencies in the measurements and to identify outliers and extreme values. Likewise, if necessary, statistical adjustments will be made. Intention-to-treat analysis will be performed.

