PTK (IE global)	Dependent	Quantitative	Continuos, Ratio	IE (***)formula)	FOCOS
Executive functions "component" 1	Dependent	Quantitative	Discrete, interval Continuos, Ratio	Number of Hits/Errors Time (sec, min)	Tower of Hanoi
Problem solving "component" 2	Dependent	Quantitative	Discrete, interval	Number of Hits/Errors	Tower of Hanoi

Cognitive flexibility			Continuous, Ratio	Time (sec, min)	
"Component" 3 Impulse control	Dependent	Quantitative	Discrete, interval	Number of Hits/Errors	Stroop test
"component" 4 Visuospatial working memory	Dependent	Quantitative	Discrete, interval	Number of Hits/Errors	Corsi Cubes
"Component" 5 Executive Attention	Dependent	Quantitative	Continuous, Ratio	Time (sec, min)	Trail Making Test (TMT)
"component 6" Sustained attention	Dependent	Quantitative	Discrete, interval	Number of Hits/Errors	Crossing out boxes
			Continuous, Ratio	Time (sec, min)	
Age	Confounding	Quantitative	Continuous, Ratio	Years and months	Survey
Sports age	Confounding	Quantitative	Continuous	Years	Survey
Playing position	Confounding	Qualitative	Nominal	Lateral, Central, Midfielder, Winger, Forward	Survey
Socioeconomic	Confounding	Qualitative	Ordinal	Scale from 1 to 6	Bill of public services of the house
Educational level	Confounding	Qualitative	Ordinal	School grade	Survey
Mass	Confounding	Quantitative	Continuous, Ratio	(kg)	Scale
Height	Independent	Quantitative	Continuous, Ratio	(cm)	Stadiometer
IMC	Confounding	Quantitative	Continuous, Ratio	(kg/m ²)	Equation
Mental fatigue	Confounding	Qualitative	Ordinal	Scale from 0 to 100	Question

Notes:

*Offensive effectiveness indices (IE) = Sum of the IE of the offensive tactical behaviors/Number of categories in which the soccer player developed offensive tactical behaviors.

** Defensive IE = Sum of the IE of the defensive tactical behaviors/N° of categories in which the Soccer players developed defensive tactical behaviors

*** Global IE = Offensive IE + Defensive IE/2

Masking

People who carry out the assessments are masked (they do not know which group the athletes were assigned to). In order to carry out an adequate strategy to control information biases, the professionals who carry out the evaluations are masked (blinding). Consequently, the evaluators of the primary, secondary, and exploratory outcomes were masked as follows:

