To obtain the data, the games must be filmed with a camera and later, carry out the respective analyzes and evaluations. In the present investigation, a DJI Fly drone is used, which is positioned 20m high just behind one of the goals, this location guarantees complete visibility of the ATTs executed by the participants and full coverage of the pitch. Once all the corresponding games have been filmed, the videos are downloaded, which are

sent to the video analyst who will carry out the respective analysis and data report in the database created for this purpose. For the analysis, the video analyst will use the LINCE PLUS video analysis software (Soto et al., 2019), which is available and freely accessible.

The FOCOS units of measure are:

Volume, which corresponds to the number of times the soccer player develops tactical behaviors in each category.

The IE is determined through the following formula:

$$IE = \text{Volume of successful tactical behaviors} / \text{Number of tactical behaviors developed in each category of analysis}$$

$$\text{Offensive IE} = \text{Sum of the IE of offensive tactical behaviors} / \text{Number of categories in which the soccer player developed offensive tactical behaviors}$$

$$\text{Defensive IE} = \text{Sum of the IE of defensive tactical behaviors} / \text{Number of categories in which the soccer player developed defensive tactical behaviors}$$

$$\text{Global IE} = \text{Offensive IE} + \text{Defensive IE} / 2$$

The global IE represents the PTK of each soccer player.

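### Global IE, the score said to represent PTK, is written without brackets in both places: read literally it is offence plus half of defence, although a simple average was probably meant

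*Combined protocol and SAP*

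**What the plan says.** The notes to Table 1 (section Variables) give the rule as "Global IE = Offensive IE + Defensive IE/2". The list of FOCOS units of measure, under Information Collection Instruments, gives the same expression as a displayed formula, also without brackets, and then adds: "The global IE represents the PTK of each soccer player".

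The same notes define the two components. Offensive IE is "Sum of the IE of the offensive tactical behaviors/Number of categories in which the soccer player developed offensive tactical behaviors". Defensive IE is "Sum of the IE of the defensive tactical behaviors/N° of categories in which the Soccer players developed defensive tactical behaviors". The FOCOS section defines the IE of a single category as successful behaviours divided by behaviours performed in that category.

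Analysis of data puts all three indices through the longitudinal analysis: "To establish the behavior of the offensive, defensive, and global IE, a repeated measures design will be carried out", with four assessments.

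The protocol nowhere calls Global IE a mean, and it gives no weights, score range or worked example.

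**The concern.** This is a rule for scoring an outcome, and as written it does not give the score that its components suggest. Division comes before addition, so the divisor of 2 applies to the defensive index only. The result is on a different scale from the two indices it summarises, and offence counts double. The protocol offers no reason for that weighting, and the section on the experimental group's training says the programme aims at both offensive and defensive actions.

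Global IE is the score said to represent PTK, the outcome named in the title and objectives. According to the Masking and Data Collection Procedures sections, a video analyst records the data in Excel and a separate masked statistician analyses them. Typed as written, the expression runs without error in Excel, SPSS or R. Many of its values would lie below 1 and would not look wrong.

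**Working it through.** **Inputs from the documents.** The unbracketed formula (Table 1 notes and FOCOS section); the component definitions; 12 players per group (Sample Size Calculation, scenario 3); two-sided alpha 0.05 (Analysis of data). The protocol gives no Global IE value, so there is no stated figure to reproduce.

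**Scale.** A category IE is a proportion, so it lies between 0 and 1. Offensive IE (O) and Defensive IE (D) average such proportions, so they also lie between 0 and 1.

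- Literal: L = O + D/2. Maximum 1 + 0.5 = 1.5; weights 1 and 0.5, a ratio of 2:1.
- Averaged: A = (O + D)/2. Maximum 1; weights 0.5 and 0.5.
- Gap: L − A = O/2. It varies from player to player, so L is not a rescaling of A.

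**Ranking (assumed values).**

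| O | D | Literal | Averaged |
|---|---|---|---|
| 0.8 | 0.4 | 1.00 | 0.60 |
| 0.4 | 0.8 | 0.80 | 0.60 |
| 0.6 | 0.6 | 0.90 | 0.60 |

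Three players who tie on the average get three different literal scores.

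**Standardised effect and power.** Assume that O and D have equal SDs, set to 1, with correlation r, and that the group effects are a on offence and b on defence, in SD units. Then

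- literal d = (a + b/2) / √(1.25 + r)
- averaged d = ((a + b)/2) / √(0.5 + 0.5r)

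For r = 0 and b = 1 only, literal d = 0.5/√1.25 = 0.447 and averaged d = 0.5/√0.5 = 0.707. Power is for a two-sample t test with 12 per arm. This is a simple comparison at one time point, not the planned repeated-measures analysis.

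| Effect (SD units) | r | d literal | d averaged | Power literal | Power averaged |
|---|---|---|---|---|---|
| 0.5 on both | 0 | 0.67 | 0.71 | 35% | 38% |
| 0.5 on both | 0.5 | 0.57 | 0.58 | 26% | 27% |
| 1 on defence only | 0 | 0.45 | 0.71 | 18% | 38% |
| 1 on defence only | 0.5 | 0.38 | 0.58 | 14% | 27% |
| 1 on offence only | 0 | 0.89 | 0.71 | 55% | 38% |
| 1 on offence only | 0.5 | 0.76 | 0.58 | 43% | 27% |

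**Agreement of the two scores.** With unit variances their covariance is 0.75(1 + r), so their correlation is 0.75(1 + r) / √[(1.25 + r)(0.5 + 0.5r)]. That is 0.95 at r = 0 and 0.98 at r = 0.5.

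**Change of sign.** Suppose offence gains g and defence loses x. The average falls if x > g; the literal score rises if x < 2g. The signs therefore differ only when g < x < 2g. For example, g = 0.05 and x = 0.08 give (0.05 − 0.08)/2 = −0.015 averaged and 0.05 − 0.08/2 = +0.010 literal. The mirror case, an offensive loss with a defensive gain, behaves in the same way. If both indices move in the same direction, no change of sign is possible.

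**Sample size.** The calculation rests on a mean difference of 1.13 and an SD of 0.81 from a cited study and does not use the Global IE formula. A t-based calculation returns 10, 11, 12, 15 and 20 per arm for the five powers, as stated.

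**The case against.** The strongest reply is that this is a slip of notation that nobody would act on. A divisor of 2 after two terms is easily read as a two-component mean. The analyst is trained in FOCOS, the coach who supervises the test consulted its author, and nothing shows that anyone scores from this line. That stands as a reason to think harm unlikely. It does not make the written rule correct.

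A second reply is that reading the PDF by program may have flattened a stacked fraction. That is possible for the displayed formula in the FOCOS section. It is less likely for the table note, where the slash is inline, and the two agree.

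A third reply is that the consequence is small and reversible. Much of this stands. The two scores are highly correlated, an equal response gives almost the same power, and Offensive and Defensive IE are analysed separately. Global IE is a fixed function of those two, so a miscoded value can be recomputed.

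A reader might infer more: that the literal formula generally costs power, that it is likely to reverse the group comparison, or that the protocol states an average and then miswrites it. The documents support none of these. Power falls for a defence-only effect but rises for an offence-only one. A reversal needs opposite movements within a narrow window. The average is a strong inference, not a statement in the text, and no scored data are shown.

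**Conclusion.** The point holds as a defect in a written scoring rule that should be corrected. As printed, Global IE is O + D/2, which gives a 0-to-1.5 range and 2:1 weighting that the protocol neither states nor justifies. It matters only if the formula is coded as written, and then mainly if offence and defence respond differently. In that case the power for a 1-SD effect on one component shifts by about 20 percentage points down (defence only) or 17 points up (offence only) with independent components, and by 13 and 16 points at a correlation of 0.5. If both respond equally, by 0.5 SD each, the shift is 3 points or less at these correlations. These sizes rest on assumed effects, equal SDs and assumed correlations, because the documents report no IE values. The design, the sample size and the two component indices are untouched.

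**What to change.** In the Table 1 notes and in the FOCOS units of measure, write Global IE = (Offensive IE + Defensive IE)/2, range 0 to 1. If the instrument's own rule really is 2:1, keep the literal form but state the weights and the 0-to-1.5 range, and justify them. The sponsor should confirm which applies against the instrument's source.

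Then check the formula in the scoring database. The Data Collection Procedures section reports that the pretest has been carried out, so the check should cover any pretest scores already computed as well as all follow-up scores. Where the formula is wrong, recompute Global IE from the stored Offensive and Defensive IE. Settle this before any results by group are seen.

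The cost is a wording change in two places and a check of one formula. No new measurements are needed.

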Regarding the game area in which the training sessions will be carried out through SSGs, the classification made by García et al., (2019) will be used as a reference, in which they state that for a game to be considered reduced, 34m^2 must be allocated to each player (approximately $7\text{m} \times 5\text{m}$). These authors suggest that the 3v2 SSGs should be developed in an area of approximately 168.75m^2 to 170m^2 ($12.5\text{m} \times 13.5\text{m}$). In the same way, they propose that the SSGs of 4v3 should be carried out in an area of approximately 238m^2 to 240m^2 ($15\text{m} \times 16\text{m}$). Although these authors do not propose a specific area for the SSGs 2c1, a space correspondence can be made following these same guidelines; In this way, the JER 2c1 can be developed in an area of approximately 102m^2 to 100m^2 ($10\text{m} \times 10\text{m}$). In this study, SSGs training will be carried out in the following areas:

2v1: 11.5m long and 9m wide (total: 103.5m^2), equivalent to 34.5m^2 for each player.

3v2: 14m long and 12m wide (total: 168m^2), equivalent to 33.6m^2 for each player.

4v3: 17m long and 14m wide (total: 238m^2), equivalent to 34m^2 for each player.

The characteristics of this training program are training frequency 5 times/week, plus 1 competition on weekends, frequency of stimulation of the SSGs and ATT of numerical superiority and inferiority 2 times/week, the specific training time assigned to the development of these formats and exercises will be from 30 to 42 minutes/training session and will be carried out after the set-up (warm-up). The total volume of the program is 920 minutes.

The SSGs (2v1, 3v2 and 4v3) that will take place on Tuesdays have a specific duration and can be easily controlled. However, the executions of the ATT (2v1, 3v2 and 4v3) that will be carried out on Thursdays, do not have a specific duration because it will depend on the dynamics of each repetition, which normally do not exceed 20 seconds. It is important to mention that, during the application of the stimuli (SSGs and ATT) no one from the coaching staff will provide feedback, or corrections to the soccer players in order to feedback does not become confusing variables. In addition, during the executions of the

SSGs, there will be balls and personnel around them to supply balls when they leave the pitch and, in this way, guarantee their continuity so that the training time is effective.

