In the event that one of the subgroups is missing player(s) to perform the repetitions set out in the protocol, due to any circumstance (non-attendance to the session, physical discomfort, momentary bruises, injury or unexpected situations), their replacement will be arranged with other soccer players who are not part of any of the comparison groups (GE and GC), they can be students of the IUEFD of the University of Antioquia (UdeA) with experience as soccer players and who previously know the ATT to be developed and also soccer players who are on trial within the team. For the registration, quantification and monitoring of the number of repetitions, a coach will be arranged so that each time the soccer players in each of their subgroups execute a repetition, he will write it down on forms designed for that purpose. Once the participants have completed the number of repetitions stated in the protocol, this coach will finish this part of the training.

After the specific stimuli oriented to actions and situations of numerical superiority and inferiority, the coaches will possibly perform other training stimuli not considered in the study; however, they will be asked not to perform additional JER or ATT training in numerical superiority and inferiority, nor ATT 1v1, 2v2, or 3v3 during the duration of the experiment to avoid co-interventions that could generate bias. It is important to mention that the coach who will execute the EG training program will be different from the one who will execute the CG training program to avoid intervention bias.

GC (Conventional Training of ATT in numerical equality)

The CG participants will perform conventional training. In the present study, ATTs that are performed in numerical equality in 1v1, 2v2 and 3v3 formats are called conventional training. Similarly, coaches will be asked not to carry out additional specific training with these formats, nor offensive or defensive SSGs or ATT in numerical superiority or inferiority, specifically in 2v1, 3v2, or 4v3 formats, during the duration of the study, to avoid confounding biases due to possible co-interventions. This GC training program will include individual, pair and trio ATTs.

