The characteristics of this training program are training frequency 5 times/week, 1 official competition on weekends, ATT stimulation frequency in 1v1, 2v2 and 3v3 formats is 2 times/week, the specific training time assigned it will be 40 minutes per training session and will be done after the set-up (warm-up). The total volume of the program is 960 minutes. As mentioned above, the coach that will execute the CG training program will be different from the one that will execute the GE training program. As with the provisions of the GE, for the CG a coach will also be assigned to register, quantify, and monitor the training stimuli of this group, who will record it in forms designed for this purpose.

The training sessions, both for the GE and CG, will take place on synthetic and natural grass pitches, which are in good condition to guarantee the normal development of the practices. If for some reason of force majeure, the training session cannot be carried out on the day assigned within the protocol, an attempt will be made to carry it out the following day, that is, Tuesday session would be performed on Wednesday and Thursday session would be performed on Friday, thus guaranteeing the weekly specific stimulation frequency (FEES). The exercises will be carried out with GOLTY N°5 balls.

Information Collection Instruments

To evaluate the primary, secondary, exploratory outcomes and the confounding variables, a battery of tests and protocols will be carried out, which are described below.

PTK (Offensive IE, Defensive IE, Global IE)

The PTK will be evaluated through the FOCOS test. This test evaluates all the actions in attack (21 actions) and all the actions in defense (10 actions) through which the offensive score, defensive score and total score are obtained and with these scores the IE is calculated (offensive, defensive and global) of each participant and each group.

Likewise, strengths, weaknesses, aspects to improve in each tactical behavior and/or phase of play can be determined according to the role (attacker with the ball, attacker without the ball in the center of the play, attacker without the ball outside the center of the play, defender to intervene in space, defender in the center of the play and defender outside the center of the play). Likewise, the actions are evaluated according to the subrole, in attack: ball control, driving, dribbling, passing, shooting, ball circulation and positioning

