Regarding the training plans (intervention protocols) to be compared, pilot tests of the training sessions were implemented in the same way as established in the protocols and with the same people responsible of each activity. The coaches will carry out the exercises and sessions of the GE and GC following the parameters of the stimuli, repetitions, volume, order, sequence, behavior, registration, and verification of compliance established in the protocol.

Participants will carry out the exercises and sessions as indicated by the coaches. Three weeks of training were carried out simulating the conditions described in the protocols (GE and GC). In week 1, the 2v1 JER and ATT formats were taking place, in week 2 the 3v2 SSGs and ATT formats were developed, and in week 3 the 4v3 SSGs and

ATT formats were taking place. These pilot tests were carried out with the same group under investigation during the last month prior to the start of the research.

Similarly, pilot tests of the FOCOS evaluation protocol were carried out. In this sense, the tests were carried out under the same conditions as set out in the protocol described above, on the same field, at the same time and with the people in charge of carrying out each of the activities (coaches, filming the test and assistants), in the same way, these pilot tests were carried out with the same participants with which the research will be carried out to familiarize the soccer players. Regarding the equipment, the procedures were also standardized with the same drone to be used and with the same person who will handle the drone during the investigation and, in addition, with the same implementation and clothing such as balls, demarcation cones and training bibs.

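### The ban on coach feedback is written only for the experimental sessions, so the arms may differ in feedback as well as in training format

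*Combined protocol and SAP*

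**What the plan says.** Under Interventions, in the GE subsection (Tactical Training in Numerical Superiority and Inferiority), the protocol states that "during the application of the stimuli (SSGs and ATT) no one from the coaching staff will provide feedback, or corrections to the soccer players". It gives the reason in the same sentence: "in order to feedback does not become confusing variables". The surrounding text describes GE's Tuesday small-sided games (SSGs) and Thursday technical-tactical actions (ATT).

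The GC subsection defines the comparator by format: "ATTs that are performed in numerical equality in 1v1, 2v2 and 3v3 formats are called conventional training". It limits additional work ("Similarly, coaches will be asked not to carry out additional specific training with these formats"), sets frequency and minutes, and repeats that "the coach that will execute the CG training program will be different from the one that will execute the GE training program". One GE provision is expressly carried over: "As with the provisions of the GE, for the CG a coach will also be assigned to register, quantify, and monitor the training stimuli". The subsection does not mention feedback or corrections.

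**The concern.** The protocol itself treats feedback during the stimuli as a potential confounder. A rule against it achieves its purpose only if both arms follow it. Written for one arm, it fixes feedback at zero there and leaves it undefined in the other, which can create the imbalance it was meant to prevent.

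The primary construct is scored from the share of tactical behaviours judged successful, so correction of tactical behaviour is a plausible route to the outcome. At stake is what the GE versus GC difference means: an effect of numerical superiority and inferiority formats, or a mixture of format, feedback and coach. Masking the assessors and the statistician does not help, because feedback would act before anything is measured.

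**Working it through.** **Step 1. The two intervention subsections side by side.**

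| Delivery rule | GE | GC |
|---|---|---|
| Formats | SSGs and ATT: 2v1, 3v2, 4v3 | ATT: 1v1, 2v2, 3v3 |
| Study sessions per week | 2 | 2 |
| Minutes per session; total | 30–42; 920 | 40; 960 |
| Limit on extra format work | stated | stated |
| Separate coach for each arm | stated | stated |
| Recording coach | stated | stated, carried over from GE |
| Replacing absent players | stated | not stated |
| Recording coach ends the block when repetitions are complete | stated | not stated |
| Feedback and corrections | banned | not stated |

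The ban names SSGs together with ATT. Only GE has SSGs, so the sentence describes GE's content.

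**Step 2. Does another section supply the rule?**
- Pilot Testing Procedures has the coaches of both arms work "following the parameters of the stimuli, repetitions, volume, order, sequence, behavior, registration, and verification of compliance established in the protocol". Feedback is not named there.
- Confounding Bias Control lists eight variables (age, sporting age, playing position, socioeconomic status, education, mass, BMI, mental fatigue). Feedback is not among them.
- The session forms are described as recording repetitions and training stimuli, not feedback. A difference would go undocumented.

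**Step 3. Could the analysis separate feedback from format?** Analysis of data plans repeated-measures ANOVA or Friedman tests, MANOVA, and paired and unpaired two-sample tests. None has a term for feedback or coach. With one coach delivering each arm, a coach term would in any case be identical to the arm term.

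**Step 4. Study time involved.** 12 weeks × 2 sessions = 24 sessions. For GC, 24 × 40 = 960 minutes, which reproduces the stated volume. For GE, 920 / 24 = 38.3 minutes per session, inside the stated 30–42. The ban therefore covers GE's 920 minutes, and no rule is written for GC's 960. These are programme minutes, not a dose of feedback.

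**Step 5. Scale, on assumed values only.** The documents give no effect of feedback.
- Inputs from Sample Size Calculation: difference 1.13, SD 0.81, 12 per arm. Alpha is 0.05 from Analysis of data, taken as two-sided.
- d = 1.13 / 0.81 = 1.395.
- The two-sample t calculation gives 11.85, so 12 per arm. This reproduces the plan's 24 players. Power at 12 per arm is 90.4%.
- Let feedback raise the GC mean by b SD. The expected standardised contrast becomes d − b, with noncentrality (d − b) × √(12/2) and 22 degrees of freedom.

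| Assumed b | d − b | Noncentrality | Power at planned effect | Chance of a significant difference if format has no effect |
|---|---|---|---|---|
| 0 | 1.395 | 3.417 | 90.4% | 5% |
| 0.2 | 1.195 | 2.927 | 79.9% | 7.6% |
| 0.5 | 0.895 | 2.192 | 55.4% | 21.6% |
| 0.8 | 0.595 | 1.458 | 28.6% | 46.6% |

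The last column uses b alone as the contrast. If b had the opposite sign, the GE versus GC difference would be inflated instead. The table uses the plan's sample-size model, not its repeated-measures analysis. It shows only that a moderate imbalance would matter with 24 players.

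**The case against.** The best counter-argument is that the ban was meant for both arms. It addresses the coaching staff generally, not the GE coach. GC's exercises are also called ATT. The GE subsection contains other statements that concern the whole trial, such as the separate-coach rule. The stated purpose makes sense only if the rule is common, and the Pilot Testing section binds both arms to parameters that include behaviour. The GC text is also visibly abbreviated: the rules on replacing players and on ending the block are missing too, so its silence on feedback is weak evidence of an intended difference.

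This is fair about intent, but it does not supply the rule. The sentence sits under GE and pairs ATT with SSGs that GC does not have, and two coaches working from this text could read it differently. Among the rules not repeated, this is the one whose stated purpose is to prevent confounding.

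Four stronger readings are tempting and are not supported:
- *Correction is allowed throughout GC's 960 minutes.* Silence is not permission. The protocol defines conventional training by format alone, so an everyday expectation of coach correction cannot be read into it.
- *The GE coach is silent for whole sessions.* The ban covers only the 30–42 minute stimulus block. No feedback rule is stated for the rest of training in either arm.
- *A GE benefit is most likely masked.* The documents give neither the sign nor the size of a feedback effect, nor its frequency in GC.
- *Every executive-function comparison is biased.* Some are pre-post tests within an arm, and the documents offer no link from tactical correction to those test scores.

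**Conclusion.** The point holds as a gap in the written design. The feedback rule binds GE only, and nothing in the plan extends it to GC. With one coach per arm, the arms may differ in feedback during the study stimuli as well as in format, and the planned analyses could not tell these apart. It should be corrected, but it is not fatal.

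That the rule is absent for GC is certain from the text. That feedback will actually differ is not known, and the direction and size of any bias cannot be determined from the documents. The figures for 0.2 to 0.8 SD rest on assumed shifts. The sample size of 24 is not in question.

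**What to change.** 1. Move the rule to a place common to both arms, for example: *During the study stimuli of GE and GC, no coaching staff give feedback or corrections.*
2. Have the recording coach already assigned in each arm note any feedback on the existing session form, and report the counts by arm.
3. State in the conclusion that the contrast is of programme plus coach.

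The cost is one sentence, one entry on a form already in use, and one line in the report, with no added staff. The small downside is that GC may be slightly less like everyday training. The recording coaches are not among the personnel described as masked, so the counts are a check on compliance, not a basis for adjustment.

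The pretest is described as done, while the training is written in the future tense, so the change appears still possible. If sessions have begun, give the date from which the common rule applied. Alternating the coaches between arms is not proposed: it would undo the deliberate separate-coach rule.
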